## **The exclusion criteria:**

- (a) thrombolytic therapy performed within 30 days;
- (b) patients who had undergone vascular bypass surgery before this study;
- (c) allergy or contraindication of antiplatelet drugs, anticoagulants, thrombolytic drugs and contrast agents,;
- (d) patients with obvious bleeding tendency, coagulation dysfunction, hypercoagulability and blood system diseases;
- (e) serious liver and kidney diseases;
- (f) history of hemorrhagic stroke within last month or ischemic stroke or transient ischemic attack within 2 weeks;
- (g) pacemaker implants;
- (h) patients who are pregnant, breast-feeding or planning pregnancy;
- (i) expected survival < 24 months.

**The primary endpoint** was the improvement of ABI at 6-month post-procedure.

**The secondary endpoints** included transcutaneous oxygen pressure (TcPO2), Rutherford category, numerical rating scale (NRS) score and safety.

**Safety endpoints** was the occurrence of trial-related adverse events that occurred during this trial. Possible adverse or serious adverse events during surgery: femoral artery stenosis, femoral artery dissection, thromboembolism (stroke or TIA), pus, hematoma at the puncture site, arteriovenous fistula requiring blood transfusion and/or surgical treatment, and other "serious" adverse events during the trial.

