## **Study process**

### **Visit 1 (Subject Screening):**

During this visit, cases are selected. Collect demographic data of patients, record patients' past medical history and medication, record vital signs, and collect patients' general physical examination. Blood pressure assessment, Rutherford scale, Wagner scale of diabetic foot ulcer, pain NRS score, painless walking distance PFWD examination, electrocardiogram examination, anklebrachial index (ABI), transcutaneous partial pressure of oxygen (TcPO2), foot sensory threshold measurement, thromboelastography (TEG), VUS microcirculation detection, and target vessels were performed. Color Doppler ultrasound and computed tomography angiography (CTA) were used to sign informed consent for patients who met the initial criteria. Blood biochemical tests were performed, including blood routine, liver function, kidney function, urine routine, blood lipids, coagulation function, blood electrolytes, catecholamines, glycosylated hemoglobin, angiotensin II, aldosterone, insulin, glucagon, homocysteine, blood glucose.

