#### **Visit 6 (6 months±7 days):**

The visit was considered 6 months ±7 days after surgery. Blood routine examination, renal function, liver function, coagulation function, blood lipid, blood electrolyte, catecholamine, glycosylated hemoglobin, angiotensin II, aldosterone, insulin, glucagon, homocysteine, blood pressure assessment, blood glucose, ankle-brachial index (ABI), transcutaneous partial pressure of oxygen (TcPO2), foot sensory threshold measurement, VUS microcirculation detection, blood pressure assessment, blood pressure assessment, blood pressure assessment. Rutherford scale, Wagner scale of diabetic foot ulcer, pain NRS score, painless walking distance PFWD examination, color Doppler ultrasound, computed tomography angiography (CTA), drug use and complications.

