#### **Adverse event observation**

All adverse events were observed, and detailed description of symptoms, date of occurrence, date of termination, relationship between degree and device, course of

treatment, and outcome were recorded. If fatal, disabling, teratogenic and other serious adverse events occur, regardless of whether they are related to the trial, emergency measures should be taken immediately to protect the interests of patients, and the main research unit, the ethics committee, the sponsor and the State Food and Drug Administration should be reported within 24 hours after being informed.

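### No rule says how the 6-month duplex and CTA enter the safety endpoint, so a silent stenosis of the denervated segment counts only if it is reported and judged trial-related

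*Combined protocol and SAP*

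**What the plan says.** The Study purpose section names safety as an aim. The Study design section describes an open-label randomised comparison in which only the ER+EDN arm has denervation, along the segment from the distal iliac to the proximal superficial femoral artery.

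The endpoints follow the exclusion criteria. The primary endpoint "was the improvement of ABI at 6-month post-procedure". The secondary endpoints are TcPO2 and "Rutherford category, numerical rating scale (NRS) score and safety". The safety endpoint "was the occurrence of trial-related adverse events that occurred during this trial". The list of harms begins "Possible adverse or serious adverse events during surgery: femoral artery stenosis, femoral artery dissection" and ends "and other 'serious' adverse events during the trial". Stenosis and dissection are given no threshold, imaging method or assessment time.

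The vessels are imaged twice. At Visit 1 the text, somewhat garbled, reads "Color Doppler ultrasound and computed tomography angiography (CTA) were used to sign informed consent". The Visit 6 list ends with "color Doppler ultrasound, computed tomography angiography (CTA), drug use and complications". Neither visit limits imaging to one arm or to patients with symptoms.

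On recording, the Adverse event observation section says "All adverse events were observed, and detailed description of symptoms, date of occurrence", and goes on to outcome and relation to the device. It does not mention imaging findings. Statistics and Analysis names no stenosis, patency or other imaging variable.

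**The concern.** The plan names a vessel harm and schedules the tests that can show it, but does not connect the two. Between a narrowing on a Visit 6 image and the safety result stand two human decisions: to report the finding as an adverse event, and to call it trial-related. A patient with a silent narrowing has no complaint to prompt the first. The second can be made with the arm known. Because only one arm has EDN, the same image could be attributed differently in the two arms.

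At stake is the completeness of a stated safety aim for the vessel segment that the experimental procedure acts on. The primary analysis is not affected.

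**Working it through.** **Step 1: endpoints against scheduled tests.**

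| Endpoint | Defined from the Visit 6 duplex or CTA? |
|---|---|
| ABI (primary) | No |
| TcPO2 | No |
| Rutherford category | No |
| NRS pain score | No |
| Trial-related adverse events | Only indirectly, if a finding is reported and attributed |

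ABI may reflect a narrowing indirectly. It is a limb-level haemodynamic measure and does not locate a lesion in the denervated segment, and a gain from revascularisation could mask one.

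**Step 2: can a late stenosis reach the safety endpoint?** Yes. The endpoint covers the whole trial, all adverse events are recorded, and Visits 3 to 6 collect complications. What remains is the relatedness filter and the absence of a rule for findings without symptoms.

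**Step 3: how much incomplete capture could matter (illustration only).** The plan gives no stenosis rate, no capture fraction and no allocation ratio, only 20 subjects in total. It therefore has no figure of its own to reproduce. Assumptions:
- 10 EDN patients, all imaged at Visit 6
- true rate p of stenosis in the segment: 10% or 20%
- fraction s of cases that end up counted: 1, 0.75 or 0.5, where s = 1 means every case is read from the images without error

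P(at least one counted) = 1 − (1 − p × s)^10

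| p | s = 1 | s = 0.75 | s = 0.5 |
|---|---|---|---|
| 20% | 1 − 0.80^10 = 89% | 1 − 0.85^10 = 80% | 1 − 0.90^10 = 65% |
| 10% | 1 − 0.90^10 = 65% | 1 − 0.925^10 = 54% | 1 − 0.95^10 = 40% |

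The differences between columns follow directly from the chosen s. They show the direction and scale of the loss and do not estimate it.

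**Step 4: what 20 subjects can support.** A count of 0/10 has an exact two-sided 95% upper limit of 1 − 0.025^(1/10) = 31%. With an assumed 10 per arm, Fisher's exact test at two-sided 0.05 has about 6% power for 10% against 30%. An imaging outcome can therefore only be descriptive.

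**The case against.** The strongest reply is that the plan already covers late stenosis. The safety endpoint is not confined to the procedure, the harms are listed as possible ones, the list closes with serious events at any time in the trial, and every adverse event is to be recorded. At Visit 6 the duplex, the CTA and the complications record appear in one list, so an investigator who sees a narrowing has an obvious place to note it. Most of this stands. A reader might infer from the reference to surgery that a late stenosis is excluded by its timing; the documents do not support that.

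A reader might also infer that the trial will report no stenosis while its own CTAs show one. That is a worst case. It requires staff to see a harm the plan names and not record it, or to record it and call it unrelated. The text does not prevent this, but nothing in it suggests it is expected. Likewise, open-label attribution could differ by arm; the documents do not show that it does.

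A third reply is that 20 subjects are too few. That rules out a significance test but not a table. A fourth is that other scheduled measures, such as walking distance and the Wagner scale, also feed no named endpoint. That is true, but duplex and CTA bear directly on harms that the safety paragraph names.

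**Conclusion.** The gap is real and limited. No rule says how the Visit 6 duplex and CTA enter the safety endpoint, and the relatedness filter, applied in an open-label trial, can drop a silent narrowing of the denervated segment. Capture of a late stenosis is possible but not assured.

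The size cannot be fixed from the documents. Under the assumptions shown, moving from full to half capture lowers the chance of counting at least one case from 89% to 65% at a true rate of 20%, and from 65% to 40% at 10%. The 31% upper limit for 0/10 comes from the number of patients and is the same with or without imaging. What imaging changes is the meaning of the count: stenosis present on the images, and not only stenosis that was reported and attributed. The point should be addressed, but the primary comparison does not depend on it.

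**What to change.** Add a descriptive safety outcome: stenosis at or above a threshold that the sponsor fixes in advance (for example 50% diameter reduction), or dissection, in the distal iliac to proximal superficial femoral segment on the Visit 6 duplex or CTA.

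- Assess it in every imaged patient in both arms, whatever the symptoms or judged relation to the trial.
- Tabulate separately (a) sites with no such lesion at Visit 1 and (b) sites with a lesion at Visit 1 or treated by revascularisation at Visit 2. A comparison with Visit 1 alone would hide the re-narrowing of a lesion that was opened at Visit 2, because that lesion would not count as new.
- Report n/N by arm with exact 95% intervals, with N the number imaged, and no significance test.
- Have the images read without knowledge of arm where existing staff allow.

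If follow-up is already complete and the images are stored, the same reading can be done and labelled post hoc.

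The cost is a few lines of endpoint wording, one table and some reading time. No procedure is added. The plan does not say that segment-level readings are made routinely, so that effort should be allowed for. The safety count may also look less favourable.

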## **Statistics and Analysis**

All continuous data are presented as mean  $\pm$  standard deviation (SD) or median with interquartile range. Categorical data are reported as numbers and percentages. Paired *t*-test and Wilcoxon signed-rank test were used to compare parameters at baseline and the 6-month follow-up. Student's *t*-test and Mann-Whitney *U* test were used to compare parameters between the two groups. When multiple follow-ups were analyzed, one-way repeated-measures ANOVA along with Bonferroni correction were used. Differences in categorical data between the two groups were analyzed using the chi-square test. *P* < 0.05 was considered statistically significant. All statistical analyses were performed using SPSS (version 22.0, SPSS, Chicago, USA) and GraphPad Prism 8 (GraphPad Software, San Diego, California).

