## **Study design**

This study was a prospective, single-center, open-labeled, randomized controlled trial designed to evaluate the safety and efficacy of ER combined with EDN for treating lower limb PAD. Patients who meet the following criteria were randomly assigned to the group of ER alone or ER combined with EDN. Subjects in the control group were treated with ER including PTA, DCB, and/or stenting, and patients in the ER+EDN group were treated with EDN from distal iliac artery to proximal superficial femoral artery before ER.

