## **Sample size**

1 site, 20 subjects.

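### Student's t-test between arms of 20 patients with no fixed split: if arm sizes and ABI spread both differ, its error and interval are off, and Welch's test avoids this cheaply

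*Combined protocol and SAP*

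**What the plan says.** The Statistics and Analysis section of the combined protocol and SAP covers all between-arm comparisons in one sentence: "Student's *t*-test and Mann-Whitney *U* test were used to compare parameters between the two groups". It does not say whether the t-test pools the variances, and it assigns neither test to a particular endpoint. The primary endpoint, stated after the exclusion criteria, "was the improvement of ABI at 6-month post-procedure". The significance level is 0.05.

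On arm sizes, the Study design section says that patients "were randomly assigned to the group of ER alone or ER combined with EDN", and the Sample size section gives only "1 site, 20 subjects". No ratio, blocking or number per arm appears.

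**The concern.** Student's t-test estimates one common variance from both arms. If the spreads differ, this does little harm when the arms are equal in size. If the sizes differ too, the pooled variance is weighted towards the larger arm, while the true variance of the difference is driven by the smaller one. The standard error is then too small when the smaller arm is the wider one, and too large when it is the narrower one.

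Neither condition is far-fetched here. With no stated ratio or blocking, nothing in the plan secures a 10:10 split. Patients range from Rutherford II to VI, so EDN might raise ABI in some and not in others, which would widen that arm. In a trial of preliminary efficacy the estimate and its interval carry most of the information, so an interval of the wrong width is the main loss.

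**Working it through.** **Inputs from the plan.** 20 patients (Sample size); random assignment with no ratio or blocking (Study design); Student's t-test and a 0.05 level (Statistics and Analysis).

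**Assumptions, because the plan gives no figures.** Two-sided tests; simple randomisation for the probability of each split; arm SD ratios of 1, 1.5 and 2; normal data unless stated. The plan gives no error rate, SD or power, so there is no figure of its own to reproduce.

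**1. How uneven could the split be?** With Binomial(20, 0.5):
- P(10:10) = 184,756 / 1,048,576 = 17.6%.
- P(7:13 or worse) = 2 × 137,980 / 1,048,576 = 26.3%. A given arm, for example EDN, is the small one in half of these, 13.2%.

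**2. Why the standard error goes wrong.** The true variance of the difference is s1²/n1 + s2²/n2. The pooled test targets [((n1−1)s1² + (n2−1)s2²)/(n1+n2−2)] × (1/n1 + 1/n2).
- 7:13, smaller arm with twice the SD: true 4/7 + 1/13 = 0.648; pooled (6×4 + 12×1)/18 × (1/7 + 1/13) = 2 × 0.2198 = 0.440. Ratio of standard errors √(0.440/0.648) = 0.82, so too small.
- 7:13, larger arm with twice the SD: true 1/7 + 4/13 = 0.451; pooled (6×1 + 12×4)/18 × 0.2198 = 3 × 0.2198 = 0.659. Ratio √(0.659/0.451) = 1.21, so too large.
- 10:10, SD ratio 2: true 4/10 + 1/10 = 0.5; pooled (9×4 + 9×1)/18 × 0.2 = 0.5. Ratio 1.

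**3. Error of the nominal 5% test, by simulation with no mean difference.**

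| Split | SD ratio | Student, smaller arm wider | Student, smaller arm narrower |
|---|---|---|---|
| any | 1 | about 5% | about 5% |
| 10:10 | 1.5 to 2 | 5.1-5.6% (arms equal in size) | same |
| 8:12 | 2 | 8.4% | 3.2% |
| 7:13 | 1.5 | 8.2-8.5% | 3.0-3.1% |
| 7:13 | 2 | 10.6-11.0% | 2.2-2.3% |

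Welch's test stays between 4.6% and 5.5% over all these splits and SD ratios.

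**4. Interval coverage.** For normal data this is 100% minus the error rate, whatever the true mean difference. At 7:13 a nominal 95% interval covers about 89-92% (smaller arm wider) or 97-98% (smaller arm narrower).

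**5. Averaged over splits.** Weighting each split by its binomial probability, Student's error is about 5.4% at SD ratio 1.5 and 6.1% at ratio 2. Favourable and unfavourable splits largely cancel.

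**6. Price of Welch if the spreads are equal** (true effect 1.2 SD; power of Student against Welch):
- 10:10: 71.6% against 71.1%, a loss of 0.5 points.
- 8:12: 70.0% against 68.6%, a loss of 1.4 points.
- 7:13: 67.7% against 64.9%, a loss of 2.8 points.

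**The case against.** The strongest reply is that the no-difference case in step 3 is artificial. If EDN does nothing for anyone, randomisation gives both arms the same distribution, and unequal spread does not arise. An error of 8-11% then needs EDN to help some patients and harm others so that the mean effect is zero. This stands as far as false-positive claims go. It does not remove the coverage result in step 4, which holds when EDN has a real but variable effect.

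It can also be said that the documents give neither a split nor an ABI SD, that no variance option is stated, and that the test sentence concerns parameters in general. All of this is true. The pooled version is nevertheless the ordinary meaning of the test named, and if Welch's was intended, saying so closes the point.

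A reader might infer two stronger claims, and neither is supported:
- **That an uneven split by itself makes the P value wrong.** With equal SDs Student's test stays at about 5% at every split.
- **That the t-test and Mann-Whitney often disagree, so the verdict hangs on which is reported.** With normal data they fall on opposite sides of 0.05 in about 2% of trials with no effect and equal SDs, and in 5-8% with a real effect. Higher figures, up to 19%, need strong skew. At 10:10 with no effect, reporting the better of the two raises the error only to 5.1-5.9%. Listing Mann-Whitney is also natural, since NRS and Rutherford category are among the secondary endpoints.

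**Conclusion.** The point holds as a conditional one of low severity. Student's test misstates the precision of the ABI comparison only if arm sizes and spreads both differ. The size of the problem is 8-11% or 2-3% error at 7:13 with an SD ratio of 1.5 to 2, but 5.4-6.1% averaged over simple-randomisation splits, and practically nothing at 10:10 or with equal SDs. Simple randomisation, the SD ratios and normality are all assumptions; the documents neither state them nor rule them out. The effect falls mainly on the confidence interval. The lack of a rule for which test decides is a missing detail worth settling in the same line, but it does not carry the finding.

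**What to change.** In Statistics and Analysis, replace Student's t-test by Welch's unequal-variance t-test, reported with its 95% confidence interval, for ABI and TcPO2. Name it as the one deciding analysis of the primary ABI comparison. Keep Mann-Whitney for NRS and Rutherford category, and for ABI only as a labelled sensitivity analysis.

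If a baseline-adjusted model is preferred, specify HC3 standard errors by name, because the variant matters with 20 patients. In a simulation at 7:13 with the smaller arm at twice the SD, HC0 gave 9.6% error and HC1 7.6%, while HC3 gave 5.1%.

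The cost is one line of text; SPSS and Prism, both already named in the plan, offer Welch's test. If spreads are equal, the power lost is about 0.5 points at 10:10, 1.4 at 8:12 and 3 at 7:13. Welch's test holds 5% for roughly normal data and is not a full repair under strong skew, where its error ranged from 3.1% to 11.4%.

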### **Visit 2 (0 day, Baseline):**

The visit was considered to determine the patient's admission/procedure date. For patients meeting the requirements, balloon catheter pre-dilation after DSA of the artery at the affected site, femoral popliteal artery stent implantation, balloon catheter post-dilation, and then arterial and nerve radiofrequency ablation were performed.

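### The arms are compared on improvement of ABI only by unadjusted tests, although screening ABI is collected; adjusting for it costs one degree of freedom and gains precision in many, but not all, plausible settings

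*Combined protocol and SAP*

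**What the plan says.** The primary endpoint, stated beneath the exclusion criteria, "was the improvement of ABI at 6-month post-procedure". It is not defined further. Sample size is given only as "1 site, 20 subjects", without effect size, SD, power or allocation ratio.

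Under Statistics and Analysis, the methods for continuous data are:

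- between arms: Student's "t*-test and Mann-Whitney *U* test were used to compare parameters between the two groups";
- before versus after: paired t and Wilcoxon signed-rank tests to "compare parameters at baseline and the 6-month follow-up", which do not compare the arms;
- several follow-ups: a one-way repeated-measures ANOVA, so with no arm term.

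No regression, ANCOVA or covariate is mentioned. The section allows for non-normal data, since summaries may be mean with "standard deviation (SD) or median with interquartile range".

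ABI is listed at Visit 1 (screening) and at Visit 6 (6 months). Visit 2, which carries the label Baseline, lists no ABI. The only pre-procedure ABI listed is therefore the screening value, and the plan does not name it as the baseline.

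**The concern.** An outcome framed as improvement has a pre-treatment value that probably predicts the 6-month value. The plan collects that value but does not say how, or whether, it enters the comparison of arms. At least four unadjusted analyses are left open: t or Mann-Whitney, on 6-month ABI or on absolute change. Percent change adds more. Which of these performs best depends on a correlation that is not known in advance. The 6-month value wastes information when the correlation is high, and the change score adds noise when it is low.

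With 20 subjects there is little precision to spare, even for a preliminary look at efficacy. An unadjusted estimate also shifts with a chance baseline difference between arms, and moderate differences are common at this size.

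**Working it through.** **Inputs.** From the documents: N = 20 and a 0.05 significance level. Assumed, because the documents do not state them: 10 per arm, two-sided testing, complete data, the correlation r between screening and 6-month ABI, their SDs (s0, s1) and the shape of the distribution. The plan gives no power figure to reproduce.

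**Scale of the problem.** With 10 per arm, a t-test reaches 80% power only at a difference of 1.32 SD of the tested variable.

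**Chance imbalance.** The baseline difference between arms has SD √(2/10) = 0.447 SD units. The chance that it exceeds 0.5 SD in either direction is P(|Z| > 0.5/0.447 = 1.118) = 26%. Given a 0.5 SD gap and equal SDs, the change estimate shifts by 0.5(1−r) = 0.35, 0.25, 0.15 SD and the 6-month estimate by 0.5r = 0.15, 0.25, 0.35 SD at r = 0.3, 0.5, 0.7. A valid test allows for this on average, so it is not a gain on top of the variance figures below.

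**Variance of the arm difference**, in units of the 6-month-value variance, with k = s0/s1:

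- 6-month value: 1
- absolute change: 1 + k² − 2rk
- ANCOVA: (1 − r²)(1 + 1/(N−4)) = 1.0625(1 − r²)

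The factor 1.0625 is the expected cost of estimating the slope at N = 20. Residual degrees of freedom fall from 18 to 17, and the critical t rises from 2.101 to 2.110.

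Example at r = 0.5, k = 1: change = 1 + 1 − 1 = 1.00; ANCOVA = 1.0625 × 0.75 = 0.797; ratio 0.80.

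ANCOVA variance divided by change-score variance:

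| 6-month SD / baseline SD | r=0.3 | 0.5 | 0.7 | 0.8 | 0.9 |
|---|---|---|---|---|---|
| 0.75 | 0.49 | 0.55 | 0.59 | 0.59 | 0.53 |
| 1 | 0.69 | 0.80 | 0.90 | 0.96 | 1.01 |
| 1.25 | 0.83 | 0.95 | 1.04 | 1.06 | 1.01 |
| 1.5 | 0.93 | 1.02 | 1.06 | 1.01 | 0.83 |

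Over r = 0.3–0.8, ANCOVA beats the change score across 100% of the range at SD ratios 0.75 and 1, 60% at 1.25, 29% at 1.5 and 19% at 1.75.

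Against the 6-month value the ratio is 1.06, 0.97, 0.80, 0.54 at r = 0, 0.3, 0.5, 0.7. Break-even is r = √(1 − 1/1.0625) = 0.24. The worst ratio against either t-test is 1.0625, reached at r = 0 (6-month value) or r = k (change).

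**Power (%)**, simulated with 100,000 replicates, a shift of 1 SD of 6-month ABI, normal baseline and exact Mann-Whitney (MW):

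| Errors, SD ratio, r | t 6-mo | MW 6-mo | t change | MW change | ANCOVA | rank ANCOVA |
|---|---|---|---|---|---|---|
| Normal, 1, 0.3 | 56.3 | 51.2 | 43.3 | 39.0 | 57.6 | 55.3 |
| Normal, 1, 0.5 | 56.4 | 51.4 | 56.6 | 51.5 | 65.9 | 62.3 |
| Normal, 1, 0.7 | 55.9 | 50.9 | 77.7 | 73.1 | 81.4 | 75.5 |
| Normal, 1.5, 0.5 | 56.1 | 51.1 | 66.9 | 61.9 | 65.7 | 62.1 |
| Normal, 1.5, 0.7 | 56.3 | 51.2 | 84.1 | 80.2 | 81.8 | 75.9 |
| t(3), 1.5, 0.5 | 64.2 | 65.2 | 76.2 | 82.0 | 75.7 | 79.8 |
| Lognormal (sigma 1), 1, 0.5 | 68.8 | 76.5 | 69.0 | 76.6 | 78.9 | 89.7 |
| Lognormal (sigma 1), 1.5, 0.5 | 68.6 | 76.5 | 79.1 | 92.2 | 78.8 | 89.7 |

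**Wider grid** (20,000 replicates; r 0–0.9, SD ratio 0.75–2, normal, t(3) and lognormal with sigma 0.5, 1 and 1.25):

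- In the 20 normal settings with r ≥ 0.3, ANCOVA beats both Mann-Whitney versions in all 20 and the change t-test in 13.
- In the 160 non-normal settings with r ≥ 0.3, it beats Mann-Whitney on 6-month ABI in 102 and Mann-Whitney on change in 54. Rank ANCOVA does so in 160 and 83.
- Worst cases at 1 SD: linear ANCOVA is 18 points below Mann-Whitney on 6-month ABI and 15 below Mann-Whitney on change; rank ANCOVA is 0.3 and 7 below.
- Type I error: ANCOVA 2.8–5.2%, rank ANCOVA 3.6–5.5%.

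**The case against.** The other side has a reasonable case, and much of it limits the weight of the point.

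- **The listed tests are legitimate, and no power target was set.** This stands. Nothing here is an error of validity, and 80% power is only a yardstick.
- **Improvement most naturally means change, so screening ABI would already be used.** This partly stands. The large gains against the raw 6-month value would then drop out, leaving ratios of 0.69–1.01 at equal SDs. But the plan does not say so, the choices of t or Mann-Whitney and of absolute or percent change remain open, and a change score fixes the baseline coefficient at 1 instead of estimating it.
- **The benefit can reverse.** This stands. All subjects are revascularised between the two measurements, so a wider 6-month spread or a low correlation cannot be ruled out. At SD ratio 1.5 the change t-test is ahead at r = 0.5 and 0.7. The size is lopsided, however: under normality the worst variance loss is 6.25%, against a 31% saving over change at r = 0.3 with equal SDs.
- **With skewed ABI, Mann-Whitney can be clearly better, and a secondary check gives no power back to the primary test.** This stands, and it is the main reason for medium confidence. Rank ANCOVA is not preferred as primary because under normality it falls up to 8 points below the change t-test.
- **The methods are written in the past tense.** If the analysis has been run, ANCOVA can only be supplementary.

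**Conclusion.** The concern holds. The plan states no baseline-adjusted comparison of the arms, collects the covariate it would need, and leaves the tested variable and the test open. The unadjusted tests remain valid, so this is a recommended change on grounds of precision and pre-specification, held with medium confidence.

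The case for ANCOVA is mainly robustness to an unknown correlation. With normal outcomes and equal SDs it is ahead of all four unadjusted options at r = 0.3, 0.5 and 0.7, whereas each unadjusted option is poor at some of those values. It is not best everywhere: it loses slightly to the change score for part of the range when the 6-month SD exceeds the baseline SD, loses slightly to the 6-month value below r = 0.24, and can lose substantially to Mann-Whitney when ABI is strongly skewed or heavy-tailed. Percent change was not evaluated.

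**What to change.** 1. Define the primary endpoint as absolute change in ABI from screening (Visit 1) to 6 months (Visit 6), and name the screening value as the baseline.
2. Name one primary between-arm analysis: ANCOVA of 6-month ABI on arm with screening ABI as covariate, reporting the adjusted difference with its 95% CI. The arm effect and p-value are identical if absolute change replaces the 6-month value as the outcome, because only the baseline coefficient moves (by 1). This does not hold for percent change.
3. Since the plan foresees non-normal data, choose one rank-based check in advance, either rank ANCOVA or Mann-Whitney on the change, and report it whatever the primary result.

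The cost is SAP wording and one degree of freedom; no new data are needed. Under normality the worst loss against either t-test is 6.25% of variance, or about 3 power points. With strongly skewed or heavy-tailed ABI the primary test can give up 10 points or more to Mann-Whitney (worst cases on the assumed grid 15–18 at a 1 SD effect and 20–24 at 0.75 SD), which is why the rank check must be fixed. If the analysis has already been done, report the ANCOVA labelled as post hoc.

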## **Study purpose**

To evaluate the safety and preliminary efficacy of endovascular denervation (EDN) for the treatment of patients with peripheral artery disease (PAD).

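### The paired tests and the one-way repeated-measures ANOVA cannot show what EDN adds to ER, and no between-group test or baseline adjustment is tied to the primary ABI endpoint

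*Combined protocol and SAP*

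**What the plan says.** Under Study design, patients are "randomly assigned to the group of ER alone or ER combined with EDN", so ER is common to both arms and EDN is the only planned difference. The primary endpoint, stated after the exclusion criteria, "was the improvement of ABI at 6-month post-procedure". No comparator, estimand or test is attached to it.

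Statistics and Analysis gives a list of methods without assigning them to endpoints:

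- **Within patients:** paired t-test and "Wilcoxon signed-rank test were used to compare parameters at baseline and the 6-month follow-up".
- **Between arms:** Student's t and Mann-Whitney U; the "test were used to compare parameters between the two groups". No parameter, time point or covariate is named.
- **Repeated visits:** "When multiple follow-ups were analyzed, one-way repeated-measures ANOVA along with Bonferroni correction were used".
- **Categorical data:** chi-square test between groups.

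ABI is measured at screening (Visit 1: "anklebrachial index (ABI), transcutaneous partial pressure of oxygen") and at all four follow-up visits (Visits 3 to 6). The visit that carries the label Baseline is Visit 2, whose text lists only the procedure. The screening value is therefore the only scheduled pre-procedure ABI.

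**The concern.** A paired test, or a one-way ANOVA whose factor is time, asks whether ABI changed. Revascularisation may change it in both arms, so a significant result is compatible with EDN adding nothing. The endpoint is worded as an improvement, which a before-and-after test fits at least as readily as a between-arm test, and the plan does not say which of them answers the primary question. A baseline-to-6-month P value, or the pattern of significance in the EDN arm but not in the control arm, could therefore be put forward as evidence for EDN.

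The between-arm route is also left open. Change and the 6-month value are different analyses with different power, and the choice could be made after the data are seen. With 20 patients in total, precision on this comparison is scarce, and a stated baseline adjustment would use information already collected.

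**Working it through.** **Inputs.** From the documents: 20 patients in total, significance at P < 0.05, ER in both arms, ABI at screening and at Visits 3 to 6. Assumed, because the documents do not give them: 10 per arm, two-sided testing, normal data with equal SDs, the ER effect, the EDN effect, and the correlation r between baseline and 6-month ABI. The plan gives no effect size, SD or power, so it has no figure to reproduce.

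**Step 1: paired test in one arm, no EDN effect.** With an ER shift of d SDs of change and n = 10, power is that of a noncentral t with 9 degrees of freedom and noncentrality d√10. Call it p. The arms are independent and have the same p, so significance with EDN but not with ER alone has probability p(1 − p).

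| ER shift (SD of change) | p | p(1 − p) |
|---|---|---|
| 0.5 | 0.293 | 0.293 × 0.707 = 0.207 |
| 0.7 | 0.506 | 0.506 × 0.494 = 0.250 |
| 1.0 | 0.803 | 0.803 × 0.197 = 0.158 |
| 1.25 | 0.939 | 0.939 × 0.061 = 0.057 |
| 1.5 | 0.987 | 0.987 × 0.013 = 0.013 |
| 2.0 | 0.9998 | 0.0002 |

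The product cannot exceed 0.25, so 0.7 SD is close to the worst case for equal arms. In simulation at 0.5, 0.7 and 1.0 SD, the between-arm t-test on change stayed at 5%. It was significant in only 9% to 11% of the trials that showed the discordant pattern. The pattern depends on allocation: over those three shifts it is 27% to 36% with 12 EDN and 8 control patients, and 8% to 16% with 8 and 12.

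**Step 2: one-way repeated-measures ANOVA in one arm, five time points, n = 10.** With no EDN effect and an ER shift of 0.5 or 1.0 SD of change, it is significant in 28% or 87% of simulated trials if the gain is complete by the first follow-up. If the gain builds evenly by visit, the figures are 23% and 76%.

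**Step 3: between-arm options, EDN effect of 1 SD of change.** If σ is the SD of ABI, the SD of change is σ√(2(1 − r)). Setting that to 1 gives σ = 1/√(2(1 − r)), and the ANCOVA residual SD is σ√(1 − r²).

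| r | σ | ANCOVA residual SD | Power, change | Power, 6-month value | Power, ANCOVA | ANCOVA gain over better unadjusted |
|---|---|---|---|---|---|---|
| 0.3 | 0.845 | 0.806 | 56% | 71% | 72% | 1 point |
| 0.5 | 1.000 | 0.866 | 56% | 56% | 66% | 10 points |
| 0.7 | 1.291 | 0.922 | 56% | 37% | 60% | 4 points |

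These powers are simulated and include chance baseline imbalance. ANCOVA type I error was 5%. Mean 95% CI half-widths for ANCOVA are 0.77, 0.83 and 0.88 against 0.93 for change, so 17%, 11% and 5% narrower. At r = 0.3 the better unadjusted test is the 6-month value, with half-width 0.782 against 0.771 for ANCOVA; there the gain is only about 1%.

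ANCOVA power falls with r in this table because the effect is fixed in SDs of change. Fixed at 1 SD of ABI instead, it rises: 57%, 66% and 82%, against 56% throughout for the 6-month value and 43%, 56% and 78% for change. The gain over the better unadjusted test is again about 1 to 10 points.

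**The case against.** The plan does list randomised comparisons, and they are valid. Nothing restricts them to one time point, so they could be used on 6-month ABI or at every visit. Several stronger readings are therefore tempting, but the documents do not support them:

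- **That the plan has no between-arm analysis of efficacy, or none for repeated visits.** Student's t and Mann-Whitney U are named without a time limit. What is missing is their assignment to the primary endpoint.
- **That the between-arm tests ignore baseline ABI.** A t-test on improvement would use baseline by subtraction. The plan does not say whether it does so; it can only be said that no adjustment is stated.
- **That EDN will be judged on within-arm P values.** No section says so. It is a risk the text leaves open.
- **That the high rates of significance over time are false positives.** They are correct detections of an ER effect, and the tests keep their 5% level for the hypothesis of no change over time. The error would lie in attributing the result to EDN.

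Three further points stand. The ANOVA factor is not named; time is inferred from its being one-way and applied to multiple follow-ups. The discordant pattern nearly vanishes if ER shifts ABI by 1.5 SD of change or more. The absence of an explicit baseline definition is only a labelling matter, since there is one scheduled pre-procedure ABI. The study is also small and its efficacy aim is described as preliminary, which argues for a short fix but not for leaving the primary comparison open.

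**Conclusion.** The concern holds as a gap in designation and efficiency, and should be fixed. Two of the three kinds of test listed for continuous data contain no group term (for the ANOVA, if its factor is time) and cannot isolate EDN. The third can, but is not linked to the primary endpoint, to change or the 6-month value, or to a baseline adjustment.

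If within-arm results were contrasted, the misleading pattern would arise in up to about a quarter of trials with equal arms and no EDN effect. It becomes rare when the ER effect is large; the documents do not say which case applies. The power gain from ANCOVA is modest. Its further advantage is that it removes a choice between two unadjusted tests whose ranking depends on a correlation the documents do not give. The direction of the argument follows from the design; the percentages rest on the assumptions listed above.

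**What to change.** 1. State the primary analysis as the between-arm difference in 6-month ABI, adjusted for the Visit 1 screening ABI (ANCOVA, two-sided 0.05, with 95% CI). Define baseline as that screening value. Keep the Mann-Whitney U test on change as a sensitivity analysis.
2. For ABI, TcPO2 and NRS over several follow-ups, replace the time-only ANOVA with baseline-adjusted between-arm differences and 95% CIs at each visit (ANCOVA by visit). If P values are given, apply Bonferroni over visits (0.05/4 = 0.0125 where all four are tested). A mixed model with group, visit and group-by-visit is optional. With a compound-symmetry covariance, its simulated 6-month false-positive rate was 6% to 7% when correlation faded by a factor of 0.5 to 0.7 per visit, whereas ANCOVA by visit stayed at 5%.
3. Label the paired tests and any time-only ANOVA descriptive, supporting no claim of EDN efficacy.
4. The statistics section is written in the past tense. If the data have been seen, label the new analysis post hoc and report the tests the plan now lists beside it.

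**Cost.** If the data are unseen, this is a change of wording only, since every measurement is already scheduled. ANCOVA uses one residual degree of freedom (18 to 17) and adds a little analysis work.
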